#### **ACRONYMS**

AAH Action against Hunger

CHWs Community Health Workers

CMAM Community Management of Acute Malnutrition

cRCT Cluster Randomized Control Trial

**EPINUT** Epidemiology of Nutrition Research Group of the Complutense

University of Madrid

HCs Health Centers

iCCM Integrated Community Case Management approach

iCCM+Nut iCCM approach including severe acute malnutrition treatment

INRSP Institut National de Recherche en Santé Publique

LARTES Laboratoire de Recherche sur les Transformations Economiques et

Sociales- Institut Fondamental d'Afrique Noire Cheikh Anta Diop

MAM Moderate Acute Malnutrition

MoH Ministry of Health

MUAC Mid Upper Arm Circumference

RUTF Ready-to-Use Therapeutic Food

SAM Severe Acute Malnutrition

SLEAC Simplified Lot Quality Assurance Sampling Evaluation of Access

and Coverage

SMART Standardized Monitoring and Assessment of relief and Transition

UNICEF United Nations Children's Fund

WHO World Health Organization

WHZ Weight-for-Height Z score

#### 1 INTRODUCTION

#### 1.1 RATIONALE

According to the latest estimates, 16.6 million children under-five worldwide suffer from severe acute malnutrition (SAM), making it a major public health concern. Over the past two decades there have been significant shifts in the way the world addresses SAM, changing from inpatient to outpatient treatment due to the development of Ready-to-Use Therapeutic Food (RUTF) and the Community Management of Acute Malnutrition (CMAM) protocol. However, a study in 21 low-and-middle income countries showed that CMAM programmes reach less than 40% coverage due to critical barriers such as carers' awareness of children's conditions, awareness of programme existence and high opportunity costs mainly due to distance from health centers (HC).

These challenges are not unique to SAM and public health services have sought ways of making key child survival interventions more integrated and more accessible. The integrated Community Case Management (iCCM) approach was introduced to improve uptake of services in areas where access to facility-based health services is poor. It is based on the training of non-medical Community Health Workers (CHWs) to provide selected curative services for high mortality infectious diseases. Given the influence of nutritional status on the recovery, this protocol also includes the identification and referral of SAM children. Thus iCCM has been described as logical platform and missed opportunity for increasing the coverage of uncomplicated SAM treatment and for preventing malnutrition.

Current international and national organisations recommend treating SAM and moderate acute malnutrition (MAM) in separate programmes, with different protocols and products (also managed by separate United Nations Agencies: RUTF managed by UNICEF and Ready-to-Use-Supplementary-Food or fortified corn/soy blend by the World Food Programme). This leads to a more expensive set-up of programmes which often results in a prioritization of SAM over MAM.

Evidence on the effectiveness of CHWs treating SAM has been summarized in a recent review published by our team^8. It included nine operational experiences in non-emergency contexts. Most reach 90% cure rates with default and death rates below 7% and 1.5% respectively. These results are even better than those from facility-based programmes, having the potential for early detection and thereby preventing complications. Coverage assessments were conducted in three studies, reaching 80% and cost-effectiveness was demonstrated in the two programmes which assessed it (compared with inpatient and CMAM). However, no evidence has been found on CHWs treating SAM in emergency settings.

Current evidence on the integration of SAM and MAM into the same protocol is scarce. There is one example in Angola achieving 93.8% recovery. In addition, another study at health facility-level in post-conflict Sierra Leone shows that integrating care for SAM and MAM allows reaching a 71% treatment coverage and

83% recovery for GAM (versus 55% and 79% respectively in the standard care applying two different protocols). SAM children receiving integrated management recovered faster, resulting in lower spend on RUTF (\$36 vs. \$68) whilst the cost for MAM was equal (\$12). Authors recommended this model as an alternative in humanitarian crises where time is essential since it reduces logistics complexity and is easy to deliver based on MUAC-only criteria. Another similar study ('ComPAS') is currently being implemented in South Sudan and Kenya but results are not yet available.

The study aims to provide the first evidence on iCCM+Nut in emergency contexts by comparing the effectiveness and cost-effectiveness of two different decentralized models of care for uncomplicated SAM children. As indicated by previous studies, this could lead to a significant improvement in coverage and cost saving in the proposed crisis region where access to health services is a major issue. Results would contribute to strengthening the health systems in the country, and potentially the entire subregion in dealing with SAM care during protracted nutritional crisis as well as acute ones. This project also responds directly to various research gaps identified in ELRHA's systematic review on health interventions in humanitarian crises: "most effective way of delivering nutritional programmes: health facilities vs. CHWs", "Cost-effectiveness of nutrition interventions", "Effectiveness of different models of delivering (vertical vs. integrated)" and "Coverage and early detection related to SAM treatment".

In addition, the proposed research is also based on Action against Hunger (AAH) previous experience. In 2014, in partnership with the Ministry of Health (MoH), the *Institute National de Recherche et Santé Publique (INRSP)* of Mali, and the Innocent Foundation, AAH launched a study to explore whether CHWs could successfully treat SAM in the southern region (non-crisis area). The evidence showed that CHWs are able to reach high quality of care achieving better outcomes than CMAM (cured: 94.2% vs. 88.2%; defaulted: 4.5% vs. 10.8%), increasing the coverage by two-fold (baseline: 43.9%, endline: 86.7%) and demonstrating this is a cost-effective intervention with lower costs incurred by beneficiaries. Further similar studies are ongoing in Mauritania, Niger and Kenya. A second phase of Mali's study started in 2017 to determine the most efficient method of scaling up treatment with CHWs by comparing three different models of training and supervision.

#### 1.2 STUDY CONTEXT

#### For Mali:

Northern Mali is classified as a "forgotten crisis" 17, and ranked as "High Risk" in the INFORM index for Risk Management 2019 (16th out of 191 countries). This is characterised by a deterioration of the security situation, difficult access to basic social services and exposure to climatic hazards. The Gao district population is 333,692 habitants (2018 National Statistics Institute of Mali). The Integrated Food

Security Phase Classification (IPC) in March 2018, estimated 15% of the population would be entering a food insecurity phase (Phase 2) and 8% would be entering a crisis phase (Phase 3). In 2019, this is expected to deteriorate. Prevalence rate of acute malnutrition is the highest in the country: 3.1% [1.9-4.8] for SAM and 14.2% [11.6-17.3] for Global Acute Malnutrition (GAM). These rates exceed the WHO emergency threshold for SAM (2%).

Zone intervention: District sanitaire de Gao

The study will be ipmented at 12 health areas at Gao District as listed below (Bagnadji, Boulgoundie, Magnadoue, Gadeye, Wabaria, Forgho, Tacharane, Château, Sossokoira, Zinda, Lobou, Bagoundje). Twlve iCCM site will be setted up at these areas.

For Senegal:

In Senegal, 152,798 people are currently in food insecurity crisis phase (stage 3) and it is estimated that this number will increase to 342,262 people during the next lean season (June-August 2019) - around 3% of the population. GAM and SAM prevalence rates are 8.2% and 2.1% respectively. The regions of Louga and Matam, and the department of Podo in the Saint-Louis region are new WHO's 10% GAM threshold, and Matam region has among the highest SAM rate in the country: 3.1% (1.9-5.0). Matam remains vulnerable to nutritional crises. Estimated number of children suffering from SAM in 2019 is 57,817 cases in 2019, while the SAM target is 45,438. 7,090 new SAM admissions (out of which 7% in IPF) were recorded between January and April 2019 (15.6% of annual target). Poor rainfalls and protracted food crisis (170,000 people in crisis in the Matam region in 2018) make Matam a region vulnerable to recurrent nutritional crisis.

The study will take place in the four health districts of the region: the districts of Matam, Thilogne, Kanel and Ranérou. According to the sampling strategy (see below), the study will work with 12 URENs and include 12 CHWs that are already trained in regular iCCM activities (case management of malaria, IRAs and diarrhoea, health promotion and prevention, and referrals of cases with complications).

#### 2 CONCEPTUAL FRAMEWORK

#### 2.1 RESEARCH QUESTION

Can the CHWs obtain equal or higher SAM cure rates and increase treatment coverage by using a combined/simplified protocol compared to using the current CMAM protocol in emergency context of Mali/Senegal.

#### 2.2 OBJECTIVES

#### 2.2.1 GENERAL OBJECTIVE

To assess the effectiveness, cost-effectiveness, and coverage of adding SAM treatment delivered by CHWs into the iCCM protocol in an emergency setting of Mali/Senegal.

#### 2.2.2 SPECIFIC OBJECTIVES

- ✓ To determine if CHWs can treat SAM children and respect the SPHERE standards in an emergency setting;
- ✓ To assess whether coverage increases by including SAM treatment within iCCM package delivered by CHWs in an emergency setting;
- ✓ To assess whether CHWs can effectively use a combined/simplified protocol to treat SAM children in an emergency setting;
- ✓ To analyze cost and cost-effectiveness of three different models of SAM treatment.
- ✓ To analyze the impact of integrating SAM management in iCCM on CHW workload (just for Senegal)

[figure not shown]
#### 3 METHODOLOGY

#### 3.1 GENERAL APPROACH

Study will take place from July 2019 to July 2022 with a recruitment and follow-up expected period from November 2019 to January 2021 but depending on Ethical Committees approval date.

It has been designed a cluster Randomized Control Trial (cRCT) with a non-inferiority design to compare three different protocols for SAM treatment (different diagnosis plus different RUTF dosage) as show in figure 1. A RCT design was chosen because it is considered the 'gold standard' methodology to evaluate healthcare interventions. A cluster approach is applied due to the impossibility of randomization at individual level. Although blinding is not possible for treatment providers, they will not have access to overall outcomes and children's caregiver attending health facilities are very unlikely to know in advance whether they will be receiving treatment based on standard or combined/simplified protocols.

Figure 1. Study design based on three different models of treatment of uncomplicated SAM children 6 to 59 months.

#### 3.2 EFFECTIVENESS ASSESSMENT

#### 3.2.1 SAMPLE SIZE AND CLUSTERING

The sample size was calculated for a binary outcome (recover/not recover) assuming 5% non-inferiority margin, 80% power, 95% sensitivity, a recovery rate of 75% in the control group (as required by SPHERE standards), a recovery rate of 85% in the intervention group (as assumed in the similar ComPAS study described in the introduction section).

The number of clusters required has been calculated according to Hayes and Bennett formula assuming a 0.05 intra cluster correlation coefficient (same as in the ComPAS study). Including 10% loss to follow-up, this resulted in a sample size of 576 SAM children per arm requiring 6 clusters each (96 children per cluster). Therefore, total sample will consist of 1,728 children by country.

Each cluster will correspond to one treatment provider (HC or its group of CHWs) which means that there will be 6 groups of providers by arm. However, in order to avoid final real imbalance in clusters size, the unit of randomization will be the health center with an allocation ratio of 2:1:1. Using this approach, there will be 6 HC allocated to control arm (=6 providers) and 3 HC allocated to each intervention arm with their 3 groups of CHWs (=6 providers). This allocation ratio is based on the figures from our previous studies in Mali were each CHW treated more children on average than each HC during a 12-month period. If all arms involved the same number of HC, the intervention arms would recruit many more children than the control (children from 6 HC plus those of their CHWs).

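### Each country is sized alone at 80% power, but with 3 randomised health centers per intervention arm it has about 51–74%; the power should be restated and the role of a joint two-country estimate fixed in advance

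*Protocol*

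**What the plan says.** Section 3.2.1 gives the inputs for a binary recovery outcome: "assuming 5% non-inferiority margin, 80% power, 95% sensitivity". Recovery under control is set at 75%, by reference to SPHERE, and under intervention at 85%. For clustering the protocol works from "assuming a 0.05 intra cluster correlation coefficient (same as in the ComPAS study"). It adds that "The number of clusters required has been calculated according to Hayes and Bennett formula". With 10% loss to follow-up this leads to 576 children per arm in 6 clusters of 96, and the section concludes: "Therefore, total sample will consist of 1,728 children by country".

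The same section makes the health center the unit of randomisation, in the ratio 2:1:1. Control receives 6 centers. The other arms are described as "3 HC allocated to each intervention arm with their 3 groups of CHWs", which the protocol counts as 6 providers per intervention arm.

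Section 1.2 names 12 health areas in Mali and 12 URENs in Senegal, so 24 centers in all. Arms, eligibility, outcome, margin and allocation ratio are the same in both countries. The general objective (2.2.1) concerns "adding SAM treatment delivered by CHWs into the iCCM protocol in an emergency setting of Mali/Senegal". Neither 3.2.1 nor 3.2.3 mentions country as a stratum or model term, or a joint estimate.

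**The concern.** The power claim is made per country, and it rests on 6 clusters per arm. In the intervention arms 3 centers are randomised, and the other 3 clusters are the CHW groups attached to those same centers. A center and its CHW group receive their allocation together and share a catchment, supervision and supplies, so they are unlikely to be two independent units.

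At an ICC of 0.05 with about 96–192 children per center, some 83–91% of the variance of a center's recovery rate lies between centers. Precision therefore depends on the number of centers, and recruiting more children per center adds little.

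Two things are at stake. A country may fail to show non-inferiority more often than the stated 20%, even if the assumed 10-point advantage is real. And the other country's centers offer extra precision at no recruitment cost, but if a joint estimate is added only after the country results are known, it is open to challenge as post hoc.

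**Working it through.** **Inputs (section 3.2.1).** Control recovery 0.75, intervention 0.85, margin 0.05, ICC 0.05, power 80%, loss 10%. Evaluable children per cluster: m = 96 × 0.9 = 86.4. The protocol does not state whether the test is one-sided 5% or one-sided 2.5%, so both are shown.

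**Reproducing the plan's figure.** Children per arm without clustering:

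n = (z₁₋α + z₀.₈)² × [0.75×0.25 + 0.85×0.15] / (0.10 + 0.05)², where the bracket is 0.315.

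- One-sided 5%: n = 87. Design effect = 1 + 85.4×0.05 = 5.27. Clusters = 87 × 5.27 / 86.4 = 5.31, rounded up to 6. Then 6 × 96 = 576 and 3 × 576 = 1,728, as stated.
- One-sided 2.5%: n = 110, giving 6.71 clusters, rounded up to 7 (672 children).

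The figure therefore reproduces at one-sided 5%, with the cluster size of 96 taken as given and without the additional cluster per arm of the Hayes and Bennett formula. Including that cluster gives 7 clusters (672) at one-sided 5% and 8 (768) at one-sided 2.5%.

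**Standard error in one country.** Variance of an arm's rate = p(1−p) × [1 + (m−1)×0.05] / (k×m), with k clusters of m evaluable children.

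- Center as unit, 6 v 3. Control: 0.1875 × 5.27 / 518.4 = 0.00191. Intervention, with 172.8 evaluable children per center: 0.1275 × 9.59 / 518.4 = 0.00236. SE = √0.00426 = 0.065.
- Every center and CHW group independent, 6 v 6. 0.315 × 5.27 / 518.4 = 0.00320. SE = 0.057.

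**Standard error for both countries, stratified by country.** The one-country SE divided by √2: 0.046 (12 v 6 centers) or 0.040 (12 v 12 providers). This assumes a common effect.

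**Power.** The distance to the margin is 0.10 + 0.05 = 0.15. Normal power is Φ(0.15/SE − z₁₋α). The t version uses the non-central t with between-cluster degrees of freedom (7, 10, 14 and 20 in the order of the rows).

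| Intervention v control | SE | One-sided 5%: normal / t | One-sided 2.5%: normal / t |
|---|---|---|---|
| One country, 6 v 3 centers | 0.065 | 74% / 66% | 63% / 51% |
| One country, 6 v 6 if independent | 0.057 | 84% / 79% | 76% / 67% |
| Joint, 12 v 6 centers | 0.046 | 95% / 93% | 90% / 86% |
| Joint, 12 v 12 if independent | 0.040 | 98% / 98% | 96% / 95% |

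**Combined/simplified v CMAM in CHW areas,** both at 85% recovery, center as unit. One country, 3 v 3: SE = √(2 × 0.00236) = 0.069, and t power with 4 degrees of freedom is 15% (one-sided 5%) or 8% (2.5%). Joint, 6 v 6: SE 0.049, and with 8 degrees of freedom 24% or 15%.

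**The case against.** The strongest reply is that nothing here is an error of pooling. A reader might infer that the protocol plans no joint estimate and so throws away the precision of 24 centers. The documents do not support that: they are silent on pooling, not against it. Section 3.2.3 names variables and adjusted regressions but no model, and a country term is commonly left to an analysis plan, which is not at hand. Sizing by country does not prevent a joint estimate. It is also a legitimate choice, since the uptake plan (5.2) aims to change policy at country level and section 5.1 names country-level scale-up alongside the Sahel region. The form Mali/Senegal in the objective can be read as either country or both, so it does not establish a joint aim. All of this stands.

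It can also be said that the power shortfall comes from how clusters are counted, and that on the protocol's own 6 v 6 count power is 79–84% at one-sided 5%, the level at which 576 reproduces. That is correct, and it is why both ends of the range are given. But 6 v 6 requires a center and its own CHW group to be uncorrelated, which the protocol does not justify. The power claim itself is made in the protocol and cannot be deferred.

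Finally, the joint gain assumes a common effect, while the settings differ: new iCCM sites in Mali, already trained CHWs in Senegal. This limits the joint estimate to a supporting role.

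**Conclusion.** The point holds in a limited form. The stated 80% power per country is not delivered with the randomised health center as unit: it is about 51–74%, depending on sidedness and on normal or t reference. With every provider independent it is about 67–84%. The unknown correlation between a center and its CHW group places the truth between these ranges. A country-stratified joint estimate with the center as unit would have about 86–95%, given a broadly common effect, and the protocol leaves its role unstated.

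It would be too strong to say that each country is likely to be inconclusive on intervention v control. At 51–74% power the chance of missing non-inferiority is 26–49% under the protocol's assumptions, so a conclusive result remains the more likely one. The exception is combined v CMAM in CHW areas, where power is about 8–15% in one country and only 15–24% jointly at equal 85% recovery (t-based). Pooling does not rescue that comparison.

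The figures rest on the protocol's 75% v 85%, ICC 0.05 applied at the level of the unit used, 86.4 evaluable children per provider (172.8 per intervention center), and 10% loss.

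**What to change.** In section 3.2.1:

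- State the sidedness of the test, and restate the per-country power with the health center as the unit. Show the range that follows from the unknown correlation between a center and its CHW group.
- State that each country's result stands as its own answer.
- Prespecify one country-stratified joint estimate (health center as unit, same 5-point margin) as supportive, so that it is not a second route to a claim. State its power, and report the country-specific differences and their heterogeneity beside it.
- Note that the combined v CMAM comparison in CHW areas remains poorly powered even jointly.

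The cost is wording and one additional table, with no more children or centers. The downside is that the joint estimate averages two different settings, so it cannot replace the country results.

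### Section 3.2.1 counts three randomised health centers per intervention arm as six clusters, so the stated 80% per-country power holds only under favourable assumptions that the protocol does not state

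*Protocol*

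**What the plan says.** Everything needed is in Protocol section 3.2.1. The inputs are "assuming 5% non-inferiority margin, 80% power, 95% sensitivity", "a recovery rate of 75% in the control group (as required by SPHERE standards" and "a recovery rate of 85% in the intervention group", with "assuming a 0.05 intra cluster correlation coefficient (same as in the ComPAS study" and 10% loss to follow-up. The result is 576 children per arm in 6 clusters of 96, or 1,728 children in each country.

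The cluster is then defined by provider: "Each cluster will correspond to one treatment provider (HC or its group of CHWs". The next step uses a different unit: "the unit of randomization will be the health center with an allocation ratio of 2:1:1". Control receives 6 centers, which are 6 providers. For the others the text reads "3 HC allocated to each intervention arm with their 3 groups of CHWs (=6 providers". The reason given is to balance the number of children recruited, since CHWs treated more children per provider in earlier work in Mali.

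Section 1.2 confirms the size of the frame: 12 health areas in Mali and 12 URENs in Senegal. Section 3.2.3 takes the center together with its CHWs as the exposure to be compared with the center alone.

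**The concern.** A cluster sample size formula counts units that are allocated independently. In the intervention arms a center and its CHW group are never allocated apart, so they cannot count as two such units. Each intervention arm has three randomised units of about 192 enrolled children, not six of 96. The 2:1:1 ratio balances the number of children but does nothing for the number of independent units. No allowance is made for correlation between a center and its own CHWs.

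Two things are at stake. The stated power may not belong to the design that will be run. And if the provider definition of a cluster were carried into the analysis, standard errors would be too small and non-inferiority would be declared too easily.

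**Working it through.** **Inputs (section 3.2.1).** Control rate p0 = 0.75; intervention rate p1 = 0.85; margin 0.05, so the distance to the margin is 0.10 + 0.05 = 0.15; ICC ρ = 0.05; 96 enrolled per provider, hence m = 96 × 0.9 = 86.4 evaluable. The 95% figure is read as a confidence level. Its sidedness is not stated, so one-sided 5% and 2.5% are both shown.

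**Step 1: reproduce 576.** Without clustering, n = (z_α + z_β)² × (0.1875 + 0.1275) / 0.15².
- One-sided 5%: (1.645 + 0.842)² × 14 = 86.6, so 87. Times 1.1 for loss gives 96. Design effect 1 + 95 × 0.05 = 5.75. Then 96 × 5.75 / 96 = 5.75 clusters, rounded up to 6, and 6 × 96 = 576. The figure reproduces, provided no further cluster is added.
- One-sided 2.5%: (1.960 + 0.842)² × 14 = 109.9, so 110. With 86.4 evaluable, 110 × 5.27 / 86.4 = 6.7, so 7 clusters. The figure does not reproduce.

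**Step 2: variance with a center and its CHWs linked.** Let s be the share of the ICC common to a center and its own CHWs. The protocol does not give s.
- Control: 0.1875 × (1 + 85.4 × 0.05) / (6 × 86.4) = 0.1875 × 5.27 / 518.4 = 0.001906.
- Intervention: 0.1275 × (5.27 + 86.4 × 0.05 × s) / 518.4 = 0.1275 × (5.27 + 4.32s) / 518.4. At s = 1 the bracket is 9.59, the design effect for 3 centers of 172.8.
- At s = 0: SE = √(0.001906 + 0.001296) = 0.0566. At s = 1: SE = √(0.001906 + 0.002359) = 0.0653.

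**Step 3: power, control vs intervention, per country.** Normal: Φ(0.15/SE − z). Small-sample: noncentral t with noncentrality 0.15/SE. Nine randomised centers give 7 df.

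| Share s | SE | 5%, normal | 5%, t 7 df | 2.5%, normal | 2.5%, t 7 df |
|---|---|---|---|---|---|
| 0 | 0.0566 | 84% | 77% | 76% | 63% |
| 0.25 | 0.0589 | 82% | 74% | 72% | 59% |
| 0.5 | 0.0611 | 79% | 71% | 69% | 56% |
| 0.75 | 0.0632 | 77% | 69% | 66% | 53% |
| 1 | 0.0653 | 74% | 66% | 63% | 51% |

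The plan's own premise, six independent clusters in each arm, gives 84% (normal) or 79% (t, 10 df) at one-sided 5%, and 76% or 67% at one-sided 2.5%. The like-for-like loss under full sharing is therefore 10 to 13 points at 5% and 13 to 16 points at 2.5%. Normal-approximation power at one-sided 5% crosses 80% at s of about 0.4.

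**Step 4: between the two intervention arms (3 vs 3 centers).** The protocol gives no rates for this comparison. Lending it 75% vs 85% with full sharing, SE = √(0.315 × 9.59 / 518.4) = 0.0763, and power is 63% (one-sided 5%) or 50% (2.5%) by normal approximation. With a true rate of 85% in both arms the distance is only 0.05, and power is 18% or 11%.

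**Step 5: error rate if the provider were the analysis cluster.** Normal approximation, nominal one-sided 2.5%; actual error = 1 − Φ(1.960 × SE_provider / SE_true).
- Control vs intervention, SEs from step 3: 1.960 × 0.0566/0.0611 gives 3.5% (half shared); 1.960 × 0.0566/0.0653 gives 4.5% (fully shared). With SEs taken at the margin itself (75% vs 70%), the SE is 0.0636 against 0.0701 or 0.0761, giving 3.8% and 5.1%.
- Between intervention arms: ratio √(5.27/7.43) = 0.842 gives 4.9%; √(5.27/9.59) = 0.741 gives 7.3%.

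**The case against.** The strongest reply concerns size. Sidedness is not stated, and 576 reproduces only at one-sided 5%. A reader who works only at 2.5% might blame the cluster counting for the whole gap between 80% and 51–63%. The document does not support that: at 2.5%, six truly independent clusters per arm already give only 76%, or 67% with t. This stands, and it is why both levels are shown side by side.

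A reader might also quote power near 45%. That value comes from a pooled-variance t-test on 6 vs 3 clusters. In simulation the test gives about 44% with full sharing and 48% with none, so it mostly reflects the choice of test and not the counting.

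The shared part of the ICC is unknown. Joint allocation is documented, but shared supply or other local influences are inferred. If sharing is slight and a normal reference is accepted at one-sided 5%, power stays above 80%. This stands as a limit on the size of the loss.

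Finally, a reader might infer that the trial's Type I error is inflated. The protocol defines the cluster for sizing but states no analysis level or degrees of freedom, which a statistical analysis plan may settle. The step 5 figures describe what a provider-level analysis would do. They are not an established feature of the plan.

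None of this restores six randomised units to an arm that has three.

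**Conclusion.** The point holds. The cluster used for sizing is not the unit that is randomised, and the per-country power is overstated unless three conditions hold together: one-sided 5%, a normal reference despite only nine centers, and less than about 40% of the ICC shared within a center. With t on 7 df, power is below 80% for every degree of sharing. The six-cluster premise is itself just short of 80% with t on 10 df.

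For half to full sharing, power is about 66–79% at one-sided 5% and 51–69% at one-sided 2.5%, where each range runs from t with full sharing to normal with half. These figures assume equal cluster sizes and the favourable 75% vs 85% rates. The comparison between the two intervention arms is weaker still. An analysis plan can correct the standard error, but it cannot recover the power lost by having three centers per arm.

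**What to change.** In section 3.2.1:
- Define the cluster as the randomised health center including its CHWs, and use that definition throughout.
- State that the analysis is at that level with small-sample degrees of freedom.
- State whether alpha is one-sided 5% or 2.5%.
- Restate per-country power as about 66–79% (one-sided 5%) or 51–69% (one-sided 2.5%) for half to full sharing of the ICC, and say that the share is assumed.
- Note that the comparison between intervention arms rests on 3 vs 3 centers.

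This costs wording and a less favourable power statement. It needs no extra children.

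Two options could recover power, and neither is required. A country-stratified pooled analysis (12 vs 6 vs 6 centers) has SE 0.0653/√2 = 0.0462 with full sharing, which gives 90% (normal) or 86% (t, 14 df) at one-sided 2.5%. It assumes a common effect in Mali and Senegal and changes the question of a trial sized by country, so a reader should not take it as the necessary primary test. The alternative is more centers per intervention arm. Keeping 6 control centers and the same number of children, with a normal reference and full sharing, at least 5 are needed at one-sided 5% (4 give 79%) and 9 at one-sided 2.5%. Either number exceeds the 12 areas now planned in each country.
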